1.3 Rationale

1.3.1 Rationale for conducting the study

The prevalence of baseline bone pain in contemporary trials of patients with metastatic castration-resistant prostate cancer is estimated between 2-45%. Despite the prevalence of bone pain, contemporary clinical trials have not addressed an agent's ability to palliate pain in a fashion that could be used for regulatory approval for this indication. The last agent to establish pain relief was in 1996 with mitoxantrone/prednisone.⁹ Other agents, such as Strontium-89 and Samarium-153 EDTMP, are approved to palliate painful bone metastases. However, both agents are beta-emitting bone seeking radiopharmaceuticals and therefore have been limited for concern of bone marrow toxicity. The phase II trial would label Radium-223 FDA approved for use in palliating pain with minimum damage to surrounding bone and substantially less marrow toxicity, allowing better quality of life.

Anticipated *benefits* of the treatment include the following:

- Palliation of bone pain with associated improvement in QOL
- Prolongation of overall survival, most definitively demonstrated in the randomized phase II trial
- Anti-tumor efficacy as measured by chemical parameters of bone turnover
- Minimal toxicity

Anticipated risks attributed to Ra-223:

- AEs: Gastrointestinal events (transient diarrhea, nausea and vomiting)

Radium-223

MSKCC

PCCTC LOI: c13-124

IRB#: 14-098 A (5)

- Transient reduction in neutrophil count. Mild to moderate reversible myelosuppression may occur.
- Ra-223 is a radioactive drug, and may, in the longer term (over several years), induce other primary cancers and bone marrow changes. From the data derived so far up to 2 years, there are no reports of long term toxicity.

The risk profile attributed to Ra-223 is favorable compared with available products in prostate cancer.

1.3.2 *Rationale for dosage selection*

The dose selected for this agent is (50 kBq (0.00135 mCi) (55kBq (.0015 after NIST update) administered every 4 weeks for 6 doses. This was selected based on prior studies, including the dose used in the randomized, phase III study that demonstrated a 31% reduction in the risk of death in comparison to placebo. This is the FDA-approved dose.

1.3.3 *Rationale for correlative studies*

A. Imaging

Routine imaging studies were not mandated by the ALSYMPCA trial. It is therefore not known what impact, if any, treatment with Radium-223 has on standard imaging studies, or the nature of the relationship between changes in standard imaging studies and cancer outcomes. Post-treatment changes on standard bone scintigraphy and cross sectional imaging will be systematically examined in this study, using PCWG2 criteria.¹

Unfortunately, bone scintigraphy does not demonstrate direct changes in metastatic disease, but rather on the surrounding bone. FDG has the capacity to demonstrate post-treatment changes in underlying tumor, even in bone, for patients with CRPC.¹⁰

Recently, CMS has reviewed the evidence of using FDG as a post-treatment indicator of treatment effects in CRPC, concluded that it has utility as a post-treatment indicator of treatment effects, and that use of FDG PET results in significant changes in management. Based on studies at MSKCC, CMS found that "FDG PET CT could be valuable even for assessing activity of bone metastases of prostate cancers in a large majority of patients".^{11,12}

Consequently, CMS proposed that use of FDG PET/CT when used to guide subsequent anti-tumor treatment strategy for patients with cancer of the prostate is reasonable and necessary under § 1862(a)(1)(A).¹²

Little is known about the anti-tumor effects of Ra- 223 in prostate cancer in regards to glucose metabolism evaluated by FDG PET/CT. However, twenty patients with metastatic breast cancer receiving Ra-223 were recently evaluated by FDG PET. Analysis revealed that a third of the target lesions defined as the standard uptake value (SUV_{max})>twice normal liver uptake and a diameter >15mm on PET CT showed a significant metabolic decrease (>25% reduction in SUV_{max} from baseline or complete disappearance of lesions) after 2 treatment doses.¹³ FDG PET/CT will

Radium-223

MSKCC

PCCTC LOI: c13-124

IRB#: 14-098 A (5)

be performed on patients in centers where such imaging is feasible, and in patients who consent to such additional imaging.

B. Serum Biomarkers

The primary serum biomarker that appears to be altered with Radium-223 are markers of bone turnover, more so than PSA. In study BC1-02 (33 patients received 4 doses of 50 kBq (0.00135 mCi) corresponding to (55kBq (.0015 after NIST update) . at 4 week intervals, 31 patients received placebo), results showed a significant decline in serum bone markers i.e. bone-ALP (the study primary efficacy endpoint), PSA response and a delayed time to PSA progression. Overall survival was prolonged in the Ra-223 group, with an increase in median survival time from 46 to 65 weeks (full analysis set). At 2 years, 10 of 33 of patients (30%) treated with Ra-223 were alive compared to 4 of 31 of placebo patients (13%). The results obtained with the biochemical markers for bone-turnover (bone-ALP, CTX-1, Procollagen Type I N-Propeptide (PINP)) and tumour load (PSA) support the presence of a treatment effect during the treatment period and for one to two months after the end of treatment. These data suggest that increasing treatment to six injections at 4 week intervals may further delay disease progression. A beneficial trend in the survival data supported a treatment effect, although survival data in 64 patients should be interpreted with caution.⁶ However, the ALSYMPCA trial which was a randomized phase III placebo controlled trial did show a survival advantage or 31% reduction in the risk of death with Radium-223.

C. Tiredness and Pain Interference

Tiredness will be measured via the worst fatigue item (item #3) of the Brief Fatigue Inventory (BFI), which asks patients to "Please rate your fatigue (weariness, tiredness) by indicating the one number that best describes your WORST level of fatigue during the past 24 hours," with rating via an 11-point numerical rating scale anchored by zero demarking "No fatigue" and 10 demarking fatigue "As bad as you can imagine." The BFI is a well-established and validated tool that has been used in myriad prior cancer trials.¹⁴ (See Appendix E for a copy of the Brief Fatigue Inventory, item #3)

Interference with general activity and sleep related to pain will be assessed by the item from the Brief Pain Inventory that asks patients to "Circle the one number that describes how pain has interfered with your general activity (or sleep) " using an 11-point numerical rating scale anchored by zero demarking "Does not interfere" and 10 demarking "Interferes completely" (Appendix F). This item demonstrates strong psychometric properties in prior research.¹⁵

2. OBJECTIVES

2.1 Primary Objective

The primary objective of this study is to determine the effects of pain palliation with Radium-223.

2.2 Secondary Objectives

2.2.1 To assess the impact of treatment on markers of bone turnover

Radium-223

MSKCC

PCCTC LOI: c13-124

IRB#: 14-098 A (5)

- 2.2.2 To assess the impact of treatment on PSA
- 2.2.3 To assess the impact of treatment on time to radiographic progression
- 2.2.4 To assess the impact of treatment on quantifiable imaging biomarkers assessing bone metabolism
- 2.2.5 To assess the impact of treatment on tiredness
- 2.2.6 To assess the toxicity of treatment
- 2.2.7 To assess the impact of treatment on pain interference specifically evaluating its affect on general activity and sleep as measured by the BPI
- 2.2.8 To assess the impact of treatment on time to pain progression
- 2.2.9 To assess the impact of treatment on change in analgesic use

3. PATIENT SELECTION

3.1 Target Population

Men with symptomatic metastatic castration-resistant prostate cancer.

3.2 Inclusion Criteria

To be included in this study, patients should meet all of the following criteria:

- Males aged 18 years of age and above
- Histological or cytological proof of prostate adenocarcinoma
- Castrate serum testosterone level: ≤ 50 ng/dL (≤ 1.7 nmol/L)
- Patients, who have experienced disease progression despite initial hormonal therapy, either by orchiectomy or by using a GnRH agonist in combination with an anti-androgen, must first progress through anti-androgen withdrawal prior to being eligible. The minimum timeframe to document failure of anti-androgen withdrawal will be four weeks. Patients on second-line (or beyond) hormonal maneuvers, and patients who had no PSA decline on combined androgen blockade as first line therapy, need not progress through AAW in order to be eligible.
- Known progressive castration-resistant disease, defined as:
 - Serum PSA progression defined as two consecutive increases in PSA over a previous reference value within 6 months of first treatment, each measurement at least one week apart. Serum PSA at screening ≥ 2 ng/mL
or
 - Documented appearance of new lesions by bone scintigraphy
- ECOG Performance Status of 0-2 (Appendix A: Performance Status Criteria)
- 2 or more bone metastases demonstrated on bone scintigraphy
- Pain at baseline as measured by a BPI worst pain score average of ≥ 3 . The BPI worst pain score average will be based on the worst pain scores completed by the patient in the 7 consecutive pretreatment days. A minimum of 4 days of pain scores must be completed by the patient in the 7 day window in order to calculate the average worst pain score. The investigator will optimize the subject's pain regimen prior to study entry.

Radium-223

MSKCC

PCCTC LOI: c13-124
IRB#: 14-098 A (5)

- Normal organ function with acceptable initial laboratory values:
 - WBC $\geq 3 \times 10^9 /L$
 - ANC $\geq 1.5 \times 10^9 /L$
 - Platelets $\geq 100 \times 10^9 /L$
 - Hemoglobin $\geq 9.0 \text{ g/dL}$
 - Creatinine $< 1.5 \times$ institutional upper limit of normal (ULN)
 - Bilirubin $\leq 1.5 \times$ ULN
 - AST/ALT $\leq 2.5 \times$ ULN
 - Albumin $> 25 \text{ g/L}$
- All acute toxicities as a result of any prior treatment must have resolved to NCI-CTCAE v4.0 Grade 1 or less at the time of signing the Informed Consent Form (ICF) [Note: Ongoing grade 2 neuropathy as a result of treatment with a cytotoxic chemotherapy regimen is permitted]
- Life expectancy of at least 6 months
- Willing and able to provide written informed consent and HIPAA authorization for the release of personal health information

NOTE: HIPAA authorization may be either included in the informed consent or obtained separately

- Willing and able to comply with the protocol, including follow-up visits, examinations as well as having the ability to self-report pain and fatigue using a PRO instrument
- Willingness to use adequate methods of contraception beginning at the signing of the ICF until at least 30 days after the last dose of study drug

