During the Run-In Period, subjects will self-report pain and fatigue using a PRO instrument daily for 7 days and record analgesic medication information on a paper pain medication diary to establish that their BPI average baseline pain score is ≥ 3 as measured for a minimum of 4 of the 7 days (See Appendix I for instructions). This data will be used to confirm eligibility based on pain experience. Upon confirmation of eligibility, the subject's registration will be completed and the subject must start treatment within 5 days of registration.

Radium-223

MSKCC

PCCTC LOI: c13-124

IRB#: 14-098 A (5)

If run-in requirements are not met with respect to pain score, subjects may be eligible to rescreen at a later time.

5.2 Treatment/Intervention Period (Week 1, Day 1 to Week 25, Day 169 (treatment visits have a window of ± 3 days))

Unless otherwise specified, all visit procedures are to be performed prior to Radium-223 administration on the day of the visit. Radium -223 will be administered every 4 weeks for 6 doses at a dose of (50 kBq (0.00135 mCi) (55kBq (.0015 after NIST update) Because ALSYMPACA did not assess radiographic assessments during treatment, neither radiographic progression nor PSA progression should be used to discontinue treatment. However, patients are *permitted, per FDA labeling*, to be maintained on other anti-cancer therapies in addition to Radium-223 provided that these are not changed in the midst of pain assessments. Other-cancer therapies must be initiated 4 weeks prior to the run-in period. Patients with an increase in pain of 2 points on their BPI worst pain item compared to baseline and confirmed at least 2 weeks later will be considered to be treatment failures and will be taken off trial. In the absence of clinical progression, patients will continue to receive all six treatments, and will continue treatment until clinical progression, unacceptable toxicity, or any criteria in Section 5.6 Removing Patients from the Protocol. Patients will return to the clinic every 4 weeks for the following assessments:

- Physical exam
- ECOG performance status
- Vital signs [body temperature, blood pressure, pulse, respiratory rate, weight]
- ECG (as clinically indicated – not required at every visit)
- Lab tests [hematology, serum biochemistry, PSA, bone markers (to be done at the Wk 9 and Wk 13 visit)]
- Clinician reported adverse events and concomitant medications will be monitored continuously throughout the study

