5.3 Follow-Up

- Patients will be evaluated every 3 months (+/- 1 week) until 6 months after the safety follow-up visit for a total of 2 visits or until initiation of another therapy. The following assessments will be performed at these visits:
 - ECOG Performance Status
 - Pain scale (BPI Short Form using a PRO instrument)
 - Fatigue scale (BFI item using a PRO instrument)
 - Analgesic diary
 - Lab tests [hematology, serum biochemistry, PSA]
 - Imaging Assessments: Bone scan, FDG PET (FDG will be done in consenting patients and is considered optional) , CT scan or MRI of the abdomen and pelvis and CT scan of the chest or Chest X-ray

The follow-up visit should be calculated from the date of the safety follow-up visit for Radium-223. For the pain and fatigue scale, data will be entered by the subject daily during the 7 day reporting period prior to their follow-up visit. Subjects will also update their analgesic dairy during this 7 day period as well.

Radium-223

MSKCC

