Prolongation of hospitalization is any extension of an inpatient hospitalization beyond the stay anticipated or required for the original reason for admission.

7.1.6 *Significant disability*

Disability is a substantial disruption of the patient's ability to conduct normal life functions.

7.1.7 *Congenital anomaly*

If the female partner of a male patient becomes pregnant during the course of the study, the treating physician must be notified immediately. All confirmed pregnancies must be immediately reported to Bayer and PCCTC and recorded in PCCTC Caisis EDC. All pregnancies will be followed until resolution (i.e., voluntary or spontaneous termination or birth) and assessed for congenital anomalies and birth defects. Patients receiving Ra-223 will be instructed to avoid conception for at least 6 month after last administration of Ra-223.

7.1.8 *Medical significance*

An event that is not fatal or life-threatening and that does not necessitate hospitalization may be considered serious if, in the opinion of the investigator, it jeopardizes the patient's status and might lead to medical or surgical intervention to prevent any of the above outcomes. Such medically significant events could include allergic bronchospasm requiring intensive treatment in the emergency room or at home, blood dyscrasias that do not result in inpatient hospitalization, or the development of drug dependency or abuse.

The NCI CTCAE v4.0 handbook will be used for adverse event descriptions and grading.

Follow-up of adverse events should continue until the event and any sequelae resolve or stabilize at a level acceptable to the investigator and the study site/sponsor or medical monitor.

Events that are **not** considered serious adverse events include:

- Routine treatment or monitoring of the studied indication, not associated with any deterioration in condition, or for elective procedures
- Elective or pre-planned treatment for a pre-existing condition that did not worsen
- Emergency outpatient treatment for an event not fulfilling the serious criteria outlined above and not resulting in inpatient admission
- Respite care

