11.4 Protocol Amendments

Before starting the study, the protocol must be approved by each institution's IRB or Independent Ethics Committee (IEC). Each change to the protocol document must be organized and documented by MSKCC and first approved by the MSKCC IRB/PB. Once approval of the MSKCC IRB/PB has been granted, PCCTC will distribute all non expedited amendments to the participating sites for submission to their local IRBs.

Participating sites must obtain approval for all non expedited amendments from their IRB within 90 calendar days of MSK IRB/PB approval. If the amendment is the result of a safety issue or makes eligibility criteria more restrictive, sites will not be permitted to continuing enrolling new participants until the participating site IRB approval has been granted.

The following documents must be provided to PCCTC for each amendment within the stated timelines:

- Participating Site IRB approval
- Participating Site IRB approved informed consent form and HIPAA authorization

PCCTC is responsible for submitting all participating site local IRB approvals and/or acknowledgments to MSK upon receipt.

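### The contraception criterion asks for 30 days after the last dose, but Section 7.1.7 tells the same men to avoid conception for 6 months

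*Combined protocol and SAP*

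**What the plan says.** Section 3.2 (Inclusion Criteria) requires willingness to use adequate "contraception beginning at the signing of the ICF until at least 30 days after the last dose of study drug". The inclusion list in the synopsis carries the same bullet.

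Section 7.1.7 (Congenital anomaly), within the adverse event definitions, covers pregnancy in a patient's partner. It ends: "Patients receiving Ra-223 will be instructed to avoid conception for at least 6 month after last administration of Ra-223".

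The bullet just before the contraception bullet in Section 3.2 is general: "Willing and able to comply with the protocol, including follow-up visits, examinations", and so on. It gives no contraception period.

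For timing, the Section 5 schedule places the six doses at Weeks 1, 5, 9, 13, 17 and 21. The heading of Section 5.2 gives the treatment period as "Week 1, Day 1 to Week 25, Day 169". Section 5.3 has patients followed "until 6 months after the safety follow-up visit for a total of 2 visits or until initiation of another therapy".

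**The concern.** The two statements cover the same men and the same hazard, and both count from the last dose, yet the minimum periods are 30 days and 6 months. Both are current protocol text, and no section available for review explains the difference.

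The criterion is the only place in the visible text where a stated contraception period is checked before a radioactive drug is given. Section 4.2.1 has sites confirm eligibility against Section 3 with a protocol-specific checklist, and staff completing it would naturally take the figure written in the bullet. The 6-month period appears once, under a safety-reporting heading. A man prepared to commit for 30 days but not for 6 months passes this criterion as written.

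What is at stake is consistency of a reproductive-safety precaution. The efficacy analysis is not involved.

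**Working it through.** The plan states no figure for the gap, so there is none to reproduce. The check compares the two periods and places them on the visit calendar. Visit windows are ignored.

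**Inputs**

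- Criterion: at least 30 days after the last dose (synopsis; Section 3.2).
- Instruction: at least 6 months after the last dose (Section 7.1.7).
- Dose 6: Week 21 (Section 5 schedule).
- Safety follow-up visit: Week 25, Day 169 (Sections 5.2 and 5.2.1).
- Last follow-up visit: 6 months after the safety visit (Section 5.3).
- Assumption: one month = 365.25 / 12 = 30.4375 days.

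**Gap between the two periods**

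- 6 months = 6 × 30.4375 = 182.6 days.
- Gap = 182.6 − 30 = 152.6 days, and 152.6 / 30.4375 = 5.0 months.
- With 30-day months the gap is 180 − 30 = 150 days, so the month convention hardly matters.

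The gap is the same for a patient who stops treatment early, because both periods run from his own last dose.

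**Calendar for a patient given all six doses**

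| Event | Calculation | Study day |
|---|---|---|
| Dose 6 (Week 21, Day 1) | 20 × 7 + 1 | 141 |
| Safety visit (Week 25, Day 1) | 24 × 7 + 1 | 169 (agrees with Section 5.2) |
| End of the 30-day commitment | 141 + 30 | 171 |
| End of the 6-month instruction | 141 + 182.6 | about 324 |
| Last follow-up visit | 169 + 182.6 | about 352 |

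The commitment that the criterion asks for ends 171 − 169 = 2 days after the safety visit. The instruction in Section 7.1.7 runs on to about Day 324.

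A completer's last follow-up visit comes 352 − 141 = about 211 days (6.9 months) after his last dose, which is beyond the 6-month period. A patient who starts another therapy can leave follow-up well before that, so later visits are not a guaranteed point at which to repeat the longer instruction.

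**The case against.** The strongest reply is that the two statements do not contradict each other. Each is a floor, a man who observes 6 months satisfies both, and nothing permits conception after day 30. That is correct. It limits the defect to a criterion that is too short for its purpose, but it does not remove the defect, because eligibility tests the stated minimum.

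A second reply is that all inclusion criteria must be met, and one of them is "Willing and able to comply with the protocol", of which Section 7.1.7 is part. On that reading, a man unwilling to follow the 6-month instruction is already ineligible. This has force. However, the general bullet does not mention contraception, while the specific bullet next to it names 30 days.

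A third reply is that patients may be told 6 months elsewhere. The consent form was not available for review. Nor was Appendix G on radiation safety precautions, which the contents page lists. So it cannot be shown that any patient is misinformed, and this review does not claim it. Whatever those pages say, Sections 3.2 and 7.1.7 still differ.

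Finally, absolute risk is probably low in men required to have testosterone at or below 50 ng/dL, and a changed criterion helps only future enrolees. This version was approved in February 2017, while accrual was planned to begin in January 2015 and last one year. Actual accrual status is not given. Both points support treating this as minor.

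**Conclusion.** The concern holds. As written, the contraception criterion asks for a minimum period about 153 days (5 months) shorter than the one in Section 7.1.7. It should be fixed, but it is a minor safety-consistency point with no bearing on the primary endpoint, sample size or error rates.

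The size given is the difference between two stated periods, not an estimate of harm. The documents contain no fertility or partner data, so the number of patients affected cannot be derived. The conclusion rests on the text available for review. If the consent form and Appendix G already state 6 months, the practical consequence shrinks, but the criterion would still need to be brought into line with them.

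**What to change.** In the contraception bullet of the synopsis and of Section 3.2, replace 30 days with 6 months and keep the start at consent. That satisfies Section 7.1.7 as it stands. Then check that the eligibility checklist, consent form, Appendix G and any patient instructions give the same period.

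The drafting cost is one wording change in two places. The operational cost comes from Section 11.4, which applies "If the amendment is the result of a safety issue or makes eligibility criteria more restrictive": a site could not enrol new participants until its own IRB had approved. If accrual is still open, the change can go into the next planned amendment, with sites told meanwhile to counsel patients on the 6-month period that Section 7.1.7 already requires.

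The partner-pregnancy reporting window in Section 7.1.7 need not change for this fix. For completers, follow-up already outlasts the 6-month period. For patients who leave follow-up early for another therapy it may not, and the sponsor may wish to consider that separately.
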